7.0 Risks

During the participant consent/assent process study personnel will address potential discomfort and risks associated with the study protocol. These will be included in the consent/assent form.

The following risks associated with participation in this study are perceived as low:

- venipuncture and intravenous angiocatheter placement: possible hematoma, site infection, nausea, and vasovagal syncope. These risks will be minimized by performing the procedure with the subject seated and cleaning the site with the appropriate antiseptic prior to breaking the skin.
- DEXA scan: studies of the radiation dose to patients from a total body DEXA scan have confirmed that patient radiation exposure is small compared to many other sources of exposure. For the total body fast scan mode that will be employed the average skin entrance dose is 0.2 μ Sv (62, 63). By comparison a chest x-ray is associated with a patient dose of 50 μ Sv.

The following risks associated with participation are additionally considered:

7.1 Hyperinsulinemia

The hyperinsulinemic, euglycemic clamp exposes participants to high insulin levels, potentially leading to hypoglycemia and hypokalemia. As shown in figures 6 and 8, the insulin infusion rate during the clamp will be 40 mU/m²/min. This infusion rate is anticipated to result in plasma insulin concentrations between 50 and 130 μ U/mL,(64, 65) levels that are within the range of physiological hyperinsulinemia and comparable to concentrations seen after meal ingestion.(65-67) By comparison, the most commonly used insulin infusion rate in the treatment of diabetic ketoacidosis is 0.1 U/kg/hr.(56) In a 70 kg, 1.73 m² individual, this infusion rate would equal 67 mU/m²/min, over 50% higher than the 40 mU/m²/min rate used in this study.

Nondiabetic CONTROL SUBSTUDY participants will be exposed to low levels of iatrogenic hyperinsulinemia from low doses of insulin glargine (STUDY 6-7)

and overnight IV regular insulin infusions prior to STUDY visits (STUDY 5 and 7). The insulin glargine dose of 0.2 u/kg/day was selected to induce long-term (7 days) iatrogenic hyperinsulinemia while avoiding the confounding effect of hypoglycemia. Based on a previous pharmacokinetic-pharmacodynamic study of glargine, this dose is anticipated to drop fasting plasma glucose by no more than 10 mg/dL.(68) Because insulin glargine is a long-acting insulin analog, we do not anticipate it will cause a rapid drop in plasma glucose concentrations, but rather a slow decrease over the course of hours. For short-term hyperinsulinemia, participants will receive intravenous (IV) regular insulin at 8 mU/m²/min for 8 hours overnight preceding the STUDY visit. Based on my previous research, I anticipate this dose will raise fasting plasma insulin concentrations in CONTROL SUBSTUDY participants from ≈8 µU/mL to ≈21 µU/mL, matching the average fasting insulin concentration of T1DM SUBSTUDY participants.(69)

We will use the following safety provisions to minimize risk of hypoglycemia and hypokalemia:

7.1.1 Glucose monitoring

Glucose levels will be monitored every hour during the overnight insulin infusion for T1DM participants as outlined in Appendix 1. Because CONTROL SUBSTUDY participants will receive IV insulin overnight prior to STUDY 5 and 7, we will monitor every hour in the CRC on the night preceding these studies. We will monitor plasma glucose concentrations every 5-10 minutes throughout the hyperinsulinemic clamp to guide the variable dextrose infusion and ensure euglycemia. Because of the frequent glucose monitoring, the study team can quickly detect a trend toward hypoglycemia before it actually occurs. If hypoglycemia does occur, however, this frequent monitoring allows for rapid detection of the low glucose concentration and rapid corrective treatment with an infusion of IV glucose (dextrose).

7.1.2 Correction of potential hypoglycemia

A licensed MD, NP, or PA will be on call throughout overnight CRC stay and at bedside during the clamp procedure. Concentrated dextrose will be at bedside to treat iatrogenic hypoglycemia. If hypoglycemia occurred, the study team could rapidly treat the low blood glucose. For example, a 75 mL IV bolus of 20% dextrose (15 gm of glucose) would bring glucose up above the hypoglycemic range in less than 5 minutes. CRC staff could deliver the dextrose into either of the two IV angi catheters available during the study.

7.1.3 Avoiding post-discharge hypoglycemia

KSP will counsel subjects on the risk of late hypoglycemia the evening and night following the clamp. We will advise them of the importance of

checking their blood glucose at bedtime and during the night to maintain a minimum of 120 mg/dL.

7.1.4 Monitoring CONTROL SUBSTUDY participants for hypoglycemia

CONTROL SUBSTUDY participants will take 0.2 u/kg/day of long-acting insulin glargine during the week prior to STUDY 6-7 and matched saline placebo during the week prior to STUDY 4-5. As discussed at the beginning of section 7.1 this dose is expected to decrease the fasting plasma glucose concentration by 10 mg/dL or less. Even so, the possibility of hypoglycemia in these nondiabetic control participants cannot be entirely avoided. Accordingly, these participants will monitor their glucose closely during the week prior to STUDY visits 4-7. The study will supply CONTROL SUBSTUDY participants with a conventional capillary blood glucose meter or a continuous glucose monitor (CGM). If a conventional capillary blood glucose meter is used, KSP will instruct participants to check their blood glucose each morning prior to breakfast (when they are most likely to have hypoglycemia after fasting overnight) and more often if needed at the discretion of the PI. If a CGM is used, the device will monitor glucose continuously during the week prior to STUDY visits 4-7. At the screening visit, KSP will teach CONTROL SUBSTUDY participants to identify symptoms of hypoglycemia. Should these symptoms occur, CONTROL SUBSTUDY participants will check their glucose level using either their conventional capillary glucose meter or their CGM. If the glucose is less than 70 mg/dL, participants will use the commonly-taught "Rule of 15" (<https://www.diabetes.org/diabetes/medication-management/blood-glucose-testing-and-control/hypoglycemia>) to treat the hypoglycemia. Participants will contact the study team after such an event occurs. The PI will then consider altering the insulin glargine dose or even withdrawing the participant based on his clinical judgement, in conjunction with the data safety monitor.

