5.3 Randomization

STUDY1-7 (Aims 1-2), include a longitudinal study of newly diagnosed T1DM patients during the first twelve months after diagnosis (T1DM SUBSTUDY, STUDY1-3) Because of the longitudinal nature of the T1DM substudy, no randomization process is needed for STUDY 1-3. The CONTROL SUBSTUDY investigates the effect of small doses of insulin in healthy, nondiabetic individuals over differing durations: one week (STUDY 5), one night (STUDY 6), both one week and one night (STUDY 7), and with no exogenous insulin at all (STUDY 4). Control participants will go through STUDY 4-7 in a random order. The study team will randomize participant into a treatment order group using a web-based randomization tool (<http://www.sealedenvelope.com>), a Microsoft Excel macro, or a randomization tool within Redcap.

STUDY B-C (Aim 3), is a random-order, 2x2 crossover study. On one arm, participants will consume a low-carbohydrate diet (LCD). On the other arm, participants will consume a standard carbohydrate diet (SCD). As shown in [figure 3](#), T1DM and control participants will be randomized into one of two treatment orders (“A” vs. “B”).

Random permuted blocks with a fixed size of 4 will be used to randomize patients into treatment order A (SCD then LCD) vs. treatment order B (LCD then SCD). The study team will randomize participant into a treatment order group using a web-based randomization tool (<http://www.sealedenvelope.com>), a Microsoft Excel macro, or a randomization tool within Redcap.

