6.1.1.6 Basal insulin instructions for CONTROL SUBSTUDY participants

CONTROL SUBSTUDY participants (who do not have diabetes) will inject low doses of subcutaneous insulin glargine (0.2 u/kg/day) over 7 days preceding STUDY 6 and 7 and placebo over 7 days preceding STUDY 4 and 5. The study team will show these participants how to properly perform these injections at home. Please see section 7 regarding risk mitigation measures to prevent serious hypoglycemia.

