6.1.2 Management Before and In Between STUDY 1-7 visits

Each T1DM participant's endocrinologist will manage his or her glycemic control and insulin doses before and between T1DM SUBSTUDY visits. The study team will review each T1DM SUBSTUDY study participant's insulin doses on at least a monthly basis between study visits.

Each CONTROL SUBSTUDY participant will take insulin glargine 0.2 u/kg/dose each day for seven days preceding STUDY 6 and 7 and an equal volume of a placebo injection (saline) prior to STUDY 4 and 5. The participant will be blinded to whether they are taking placebo or insulin glargine.

Although the study takes several measures to mitigate the possibility of hypoglycemia in these participants (section 7.1), the investigator will not be blinded to whether or not control participants are taking insulin prior to CONTROL SUBSTUDY participants. This enables the investigator to rapidly alter the course of the intervention in the event of hypoglycemia.

In the unlikely event severe hypoglycemia occurs (i.e. loss of consciousness or seizure due to hypoglycemia) blinding will be broken to ensure the patient's hypoglycemia is treated appropriately.

Approximately 10-14 days before STUDY visits 1-7, a study team member will contact the participant to remind them to:

1. Wear their CGM for at least the 7 days leading up to the STUDY visit for T1DM SUBSTUDY participants CONTROL SUBSTUDY participants will be reminded to wear either their study-supplied CGM or conventional capillary blood glucose monitor.
2. Record food and drink consumed for the 7 days leading up to the STUDY visit in their digital food log.

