10.0 Statistical Considerations

10.1 STUDY 1-7 (Aims 1-2)

10.1.1 Sample Size Justification

My accrual goal is to obtain an adequate number of participants within both the T1DM SUBSTUDY (STUDY 1-3) and CONTROL SUBSTUDY (STUDY 4-7) to ensure greater than 80% statistical power ($1-\beta$) for a two-sided α -level of 5% for each specific aim's primary outcome. The sample size calculations used the best-available previously published descriptions of insulin sensitivity(28, 105) and %FMD(7, 30, 106-108) in T1DM. Table 7 summarizes these calculations.

Table 7: Key parameters for sample size calculations for T1DM and CONTROL substudies. n , δ , $1-\beta$, σ , and r represent the sample size, the expected minimum difference, statistical power, overall standard deviation, and longitudinal correlation, respectively, for each key outcome. * indicates calculations based on preliminary data as previously described. [†] The detectable differences for GIR of 1.3 to 2.2 mg/kg/min represent a 20% to 21% change in outcomes. [‡] The detectable differences for %FMD of 2.2% to 4.3% represent a 25% to 39% change in outcomes.

Aim	T1DM Substudy					Control Substudy						
	Key Outcome for Power Calculation	n	δ	$1-\beta$	σ	r	Key Outcome for Power Calculation	n	δ	$1-\beta$	σ	r
1	GIR between STUDY T ^{LO} vs. T ^{HI} in mg/kg/min	20	1.3	0.88	2.7	0.79	GIR between STUDY C ^{BOTH} vs. C ⁰ in mg/kg/min	20	2.2	0.92	3.5	0.79
2	%FMD between STUDY T ^{LO} vs. T ^{HI}	20	2.2%	0.88	4.3%	0.83	%FMD between STUDY C ^{BOTH} vs. C ⁰	20	4.3%	0.83	3.7%	0.83

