10.1.2 Analysis Plan

The correlation between the independent variable TDD_{insulin} (averaged over 7 days prior to each STUDY visit) and the key dependent variable for each objective will be determined: GIR in Aim 1; %FMD and MVR in Aim 2. Several other explanatory variables could influence each specific aim's key dependent variable, however. For example, confounding variables might include hyperglycemia, hyperlipidemia, or the dependent variables in each aim could affect one another (e.g. insulin resistance could affect endothelial dysfunction). For this reason, I will use multivariable linear regression analysis to account for the effect of potential confounders, which include age, T1DM duration, glycemia (both from both CGM over 7 days and HbA1c), lipidemia (i.e. lipoprotein subclass sizes and particle concentrations), NEFA concentration, hypertension, BMI, body composition, and estrogen level.

The study accrual of 40 participants provides 3 to 4 degrees of freedom for a multivariable linear regression analysis. (i.e. TDD_{insulin} and 3 additional independent variables can be included in an adequately-powered model). To quantify the effect of potential confounders, unadjusted and adjusted linear regression models will be fit and compared for each Aim's primary outcome (GIR and %FMD). I will analyze changes in β -coefficients between unadjusted and adjusted models for scientifically significant differences.

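### Section 10.1.2 regresses the control crossover (STUDY 4-7) on insulin dose with no participant or assigned-condition term, so glargine changes or withdrawals after low glucose can bias the slope toward the hypothesis

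*Combined protocol and SAP*

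**What the plan says.** - **Design.** Section 5.3: "Control participants will go through STUDY 4-7 in a random order".
- **Assigned exposure.** Under 6.1.1.6, controls "will inject low doses of subcutaneous insulin glargine (0.2 u/kg/day) over 7 days preceding STUDY 6 and 7 and placebo" in the week before STUDY 4 and 5. Glargine exposure is therefore fixed by condition.
- **Departures from it.** Section 7.1.4 covers a control whose glucose falls below 70 mg/dL: "The PI will then consider altering the insulin glargine dose or even withdrawing the participant based on his clinical judgement". The data safety monitor is involved. Section 6.1.2 leaves the investigator unblinded to glargine and gives the reason: "This enables the investigator to rapidly alter the course of the intervention in the event of hypoglycemia". Nothing says how large a change may be, or whether it carries over to the second glargine week.
- **Analysis.** In 10.1.2 the independent variable is total daily insulin dose, "averaged over 7 days prior to each STUDY visit) and the key dependent variable for each objective will be determined". The method follows: "I will use multivariable linear regression analysis to account for the effect of potential confounders". The listed confounders include age, glycemia, lipids, BMI and body composition. No participant, period or assigned-condition term is named, and there is no rule for altered doses or withdrawn controls.
- **Sample size.** Table 7 sizes the controls on STUDY C-BOTH versus C-0, with a longitudinal correlation of 0.79 for GIR. That contrast does not reappear in 10.1.2.

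**The concern.** At a fixed glargine dose, a low glucose is more likely in someone who is insulin sensitive, and that person also has a high GIR. Cutting the dose pairs high GIR with low dose. Withdrawal drops the person's glargine visits while any completed placebo visits may stay in the data. In a regression that treats visits as unrelated, both create a negative slope between insulin dose and GIR, which is what Aim 1 expects to find.

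This matters because STUDY 4-7 is the only part of Aims 1-2 in which insulin exposure is assigned in random order. A comparison within each person by assigned condition would largely avoid the problem, and it is the comparison on which the substudy was sized.

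**Working it through.** **1. The plan's own figure.** Table 7, control GIR: n = 20, difference 2.2, SD 3.5, r = 0.79, stated power 0.92.

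- SD of a paired difference = 3.5 × √(2 × (1 − 0.79)) = 2.27.
- Standard error = 2.27/√20 = 0.51.
- Power of a two-sided 5% paired t-test = 0.984, so 0.92 is not reproduced. The stated value is lower than the inputs give, and this does not affect the present point.
- The T1DM GIR row does reproduce by the same method (0.883 against 0.88). This supports reading Table 7 as a paired comparison.

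**2. Model with no insulin effect.** GIR = person effect + visit error.

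- Person variance = 0.79 × 3.5² = 9.68 (SD 3.11). Visit variance = 0.21 × 3.5² = 2.57.
- Glargine dose is 0, 0, 0.2 and 0.2 u/kg/day for STUDY 4 to 7. The overnight infusion is left out. At 8 mU/m²/min for 8 hours, in a 70 kg, 1.73 m² person, it adds only about 0.014 u/kg/day to a 7-day average.
- Assumptions not in the documents: 1 to 4 of 20 controls are affected, and their tendency to lows correlates 0.5 to 1.0 with the person effect.
- Reported quantity: 0.2 × the least-squares slope of GIR on dose, controls only, no participant term.

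**3. Results (mg/kg/min per 0.2 u/kg/day, true value 0).**

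| What happens to affected controls | Bias | Share of 2.2 |
|---|---|---|
| Glargine halved from a random day of the first glargine week, then carried over | -0.11 to -0.66 | 5% to 30% |
| Withdrawn in the first glargine week, random order, later visits lost | -0.06 to -0.40 | 3% to 18% |
| Only completers analysed after such withdrawals | 0.00 | 0% |
| No dose change or withdrawal | 0 | 0% |

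**4. Hand check of the upper end of the first row.** Four of 20 controls are affected and the correlation is 1.0.

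- The top 4 of 20 standard normal values average about 1.33, so these people lie 1.33 × 3.11 ≈ 4.15 above the mean GIR.
- With 4 of 7 days at full dose, the first glargine week averages 0.2 × 4/7 + 0.1 × 3/7 = 0.157. The second is 0.1.
- Mean dose over four visits is (0.157 + 0.1)/4 = 0.064 for them and 0.1 for the others.
- Covariance of dose and GIR = 0.2 × (0.0643 − 0.1) × 4.15 = -0.0296.
- Mean dose = 0.8 × 0.1 + 0.2 × 0.0643 = 0.0929. Mean squared dose = 0.8 × 0.02 + 0.2 × (0.157² + 0.1²)/4 = 0.0177. Dose variance = 0.0177 − 0.0929² ≈ 0.0091.
- Bias = 0.2 × (-0.0296/0.0091) ≈ -0.65, in line with the simulated -0.66.

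**5. Which part of the model matters.**

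- If stable sensitivity drives the lows, a participant term alone brings the slope within 0.02 of zero, even on dose taken.
- If that week's sensitivity drives them, a participant term with dose taken leaves -0.05 to -0.4.
- With a participant term and assigned dose, the bias is within 0.02 of zero when visits are kept. If that week's sensitivity causes glargine visits to be lost, -0.10 to -0.28 remains at event rates of 5% to 20%.

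**The case against.** **The event rate is unknown and may be near zero.** Section 7.1 says the dose was chosen to avoid hypoglycemia, 7.1.4 expects fasting glucose to fall by 10 mg/dL or less, and the investigator need only consider a change. This stands: the bias is conditional. Section 7.1.4 also accepts that hypoglycemia cannot be ruled out entirely.

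**Section 10.1.2 does not say that a control's dose is the dose taken.** Correct. It is the natural reading of a 7-day average before each visit, and the text should settle it.

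**The planned model may pool both substudies.** Section 10.1.2 states: "The study accrual of 40 participants provides 3 to 4 degrees of freedom for a multivariable linear regression analysis". In a pooled 40-participant model, at 5% to 20% events with glargine halved or stopped, dose changes add only about -0.01 to -0.10 without a group term and -0.08 to -0.47 with one. This stands, so the step 3 figures apply to a controls-only fit.

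**The glargine rule is not the root cause.** This also stands. The main gap is the missing participant term, and assigned condition adds protection when weekly sensitivity drives dose changes.

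**Stronger readings that a reader might infer.**

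- *The randomised comparison is lost.* It is not. Every control is assigned all four conditions, so the contrast can still be analysed.
- *Withdrawn controls contribute placebo visits only.* Order is random, so they also lose later placebo visits and may contribute none.
- *The bias approaches -0.93 or -1.04.* Those values need the dose halved throughout both glargine weeks, or every glargine visit lost with every placebo visit kept. Neither follows from 7.1.4, where a change comes after a low glucose.

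**Conclusion.** The point holds as a conditional weakness in the analysis plan. Section 10.1.2 does not carry Table 7's within-person contrast into the analysis, and its regression on dose has no participant or assigned-condition term. Given the discretion in 7.1.4, a controls-only fit can be biased toward the study's hypothesis, by about -0.11 to -0.66 mg/kg/min (dose halved) or -0.06 to -0.40 (withdrawal) per 0.2 u/kg/day.

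These sizes rest on the assumed 1 to 4 affected controls of 20, on those controls being the more sensitive ones, on reading the dose as dose taken, and on partial data from withdrawn controls being used. The documents do not show that a false slope will occur. They show that the planned model would not prevent one.

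**What to change.** In 10.1.2:

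1. Make the primary analysis of STUDY 4-7 a within-participant comparison by assigned condition, with participant and period terms and C-BOTH versus C-0 as the key contrast.
2. Keep visits with altered glargine under their assigned condition.
3. Use all available visits from withdrawn controls, and report dose changes and withdrawals by condition.
4. Report the regression on insulin dose in controls as supportive, stating whether dose means taken or assigned.

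Fix this wording before outcome data are examined, because the investigator who may change doses is unblinded. Before conditions are coded, reconcile 5.3 with 2.0, 6.1.1.6 and 6.1.3.4, which disagree on which of STUDY 5 and STUDY 6 is the one-week and which the one-night condition.

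The cost is a few sentences and slight dilution of the glargine effect: if 3 of 20 take half the dose and the effect is proportional to dose, 3/20 × 0.5 = 7.5%. Most of the bias is removed, but some can remain if that week's sensitivity causes visits to be lost. The safety rule in 7.1.4 is unchanged.

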7.1.5 Safety provisions to minimize hypokalemic risk

Hyperinsulinemia causes extracellular potassium to shift into the intracellular space, a factor that could contribute to apparent hypokalemia. Vital signs will be monitored throughout the STUDY visit procedure. Potassium will be monitored using bedside iStat monitor. Oral potassium replacement will be given as needed at the discretion of the PI or his designated MD, NP, or PA KSP.

7.2 Risks Associated with Perflutren Lipid Microsphere Infusion

7.2.1 Clinical and Research Application of Perflutren

Perflutren is an ultrasound contrast agent indicated for clinical use in patients with suboptimal echocardiograms to opacify the left ventricular chamber and improve the delineation of the left ventricular endocardial

border.(70) This agent was initially FDA approved in 2001 and in Europe indications also include the detection and characterization of liver and breast masses as well as for Doppler enhancement and the assessment of vasculature.(71)

Current ultrasound contrast agents, including perflutren, consist of microbubbles of an inert, relatively insoluble gas encapsulated by an outer lipid shell. Perflutren (octafluoropropane) is a high-density, high-molecular weight gas that exhibits low solubility. The mean diameter of a microsphere ranges between 1.1-3.3 μm ,(70) which allows passage from the peripheral injection site into the systemic circulation, but prohibits passage through the endovascular borders. Thus, the microspheres remain as intravascular indicators. When coupled with ultrasound, the microspheres induce a large alteration in the acoustic impedance reflection patterns within tissue or blood. As a result, there is a marked increase in the signal-to-noise ratio, which enhances ultrasound signals and provides a dramatic improvement in the vascular imaging quality.(71)

The use of ultrasound contrast agents in diagnostic imaging extends beyond the currently approved indications as well. Increasingly, perflutren is used in human subjects' research to study changes in microvascular blood volume in muscle and adipose tissue.(40) More recently, contrast-enhanced ultrasound with perflutren quantified insulin-stimulated changes in vasodilation in healthy young adults (72) and individuals with T1DM.(73) Our study will quantify how much decreasing chronic iatrogenic hyperinsulinemia improves insulin-stimulated increases in microvascular blood volume in T1DM using this technique.

